6.7 ASSESSMENT OF SUBJECT COMPLIANCE WITH STUDY INTERVENTION/INVESTIGATIONAL PRODUCT

Subjects should be instructed to return all unused study medication and containers at each clinic visit during the clinical trial period so that drug accountability can be performed. The dispensing pharmacy is required to count all returned study capsules and record this on the proper CRF.

All study medication returned by subjects must be accounted for and verified by the study research nurse clinician and research pharmacist. After verification of all study medication, used packages and unused study medication will be returned to GTx, Inc., or authorized representative.

Treatment Compliance

Study subjects should be counseled on the need to meet 100% compliance with taking study drug. The investigator or designee should ensure that study subjects meet this goal throughout the study period. Compliance will be verified by the accounting of study drug at each in person visit after baseline. When study drug is administered at the research facility, it will be administered under the supervision of study personnel. Compliance with taking study drug will be monitored by the accounting of unused medication returned by the subject at visits. Compliance will be documented. If compliance is less than 80% or more than 120%, the Investigator or designee is to

counsel the subject and ensure steps are taken to improve compliance. Subjects who are less than 80% or more than 120% compliant with the dosage regimen for any two consecutive visit periods during the study may be withdrawn from the study.

6.8 CONCOMITANT MEDICATIONS/TREATMENTS

Forbidden medications and treatments during the study duration include:

- Systemic hormonal products including but not limited to estrogens, progestins, testosterone, methyltestosterone, oxandrolone (Oxandrin[®]), oxymetholone, danazol, fluoxymesterone (Halotestin[®]), other androgenic compounds, including herbals. Intravaginal application of estradiol topical/tablet agents and hormones delivered via vaginal ring are allowed.
- Treatment with any investigational agent within 6 months before the first dose of study treatment;

Previous and Concomitant Medication (Drugs and Therapies)

The Investigator or designee must record the use of previous (all medication taken within 30 days prior to Screening (Visit 1) and current concomitant treatment, both drug and non-drug therapies, prescribed and over-the-counter and all alternative medicines, in the CRFs. This also includes drugs used on a chronic and as-needed basis. Subjects must be instructed not to start any new medication, both prescribed and over-the-counter, without consulting the Investigator, unless the new medication is required for emergency use. Subjects must be instructed to notify the Investigator immediately if medications were required for emergency use.

7. STUDY SCHEDULE

7.1 STUDY VISITS

Each subject may complete up to 5 months of study participation.

Screening Visit, Days -21-0

The study will be explained in detail and adequate time will be allowed for answering potential subjects questions prior to signing the IRB approved informed consent document. Informed consent will be obtained from those volunteers meeting initial inclusion/exclusion criteria and expressing willingness to participate prior to conducting any further study tests or measures.

Once informed consent is obtained, a detailed interview with vital signs will be conducted to further review for inclusion/exclusion criteria. A subject number will be assigned. Height and weight will be measured. Subjects will complete the MESA questionnaire to assess incontinence type (stress, urge, or mixed). If urinary incontinence type is stress predominant, then the subject will be instructed to complete a 24 hour pad weight and 3 day voiding diary prior to the next study visit. A bladder

stress test will be done to confirm SUI. Lab tests will also be drawn at this visit as outlined in Table I. A baseline urinalysis will be obtained. Concomitant medications will also be assessed and recorded.

Additional Screening, Days -21-0

If the subject has qualified for the study during the Screening visit, the following procedures will be performed between Screening Visit and Visit 1. Mammogram, if not done within the last 6 months, will be performed. Pelvic MRI will be performed

Study Visit 1: Week 0, Clinic Visit

Subjects still meeting inclusion/exclusion criteria after all Screening study measures have been completed and reviewed will return for Visit 1 where the 24 hour pad weight and 3 day voiding diary will be collected and reviewed. An interview with vital signs will be conducted. A detailed medical history will be taken, including past gynecological and obstetric history (gravida, para, prior abortions and deliveries) and a focused physical exam, including standard gynecological pelvic exam and skin assessment, will be done. Urine dipstick will be done and PVR will be measured. If subject still meets inclusion/exclusion criteria, UPP will be performed. A dose of Ciprofloxacin or equivalent will be given prophylactically to prevent bladder infection. Serum lab tests consisting of a CBC, lipid panel and testosterone level will be drawn. Questionnaires (UDI-6, IIQ, FSFI, and PGI-S) will also be completed at this visit. Concomitant medications and adverse events, will be assessed and recorded. A baseline MRI measurement will be scheduled and/or completed prior to receiving study drug.

Subjects who meet all the inclusion and none of the exclusion criteria will receive study drug. Study drug will be packaged in bottles. Each study drug bottle will be preprinted with a Medication ID number. The Medication ID number assigned to the subject will be noted in the case report form (CRF) for study drug.

The first dose of study drug will be taken during this visit if the subject meets all criteria for enrollment. A one month supply of study drug (35 count bottles) will be dispensed with administration instructions.

Study Visit 2: Week 1, Phone Call

Approximately 1 week after beginning treatment, subjects will be contacted by phone to assess for concomitant meds and adverse events. Subjects will also be instructed to complete a 24 hour pad weight and 3 day voiding diary within the week preceding their next study visit.

Study Visit 3: Week 4, Clinic Visit

Approximately 4 weeks after beginning treatment, subjects will return to the clinical research office for an in person visit. An interview with vital signs will be conducted. Height and weight and PVR will be measured. Pad weights will be measured, and the 3 day voiding diary will be collected and reviewed. Blood will also be drawn to measure serum AST, ALT, and total bilirubin. Questionnaires will also be completed, and

concomitant meds and adverse events, including any vaginal bleeding, discharge, infections and/or spotting, will be assessed and recorded. Subjects will also be instructed to complete a 24 hour pad weight and 3 day voiding diary in the week preceding their next study visit. A 30 day supply of study drug will be dispensed with administration instructions.

Study Visit 4: Week 8, Clinic Visit

Approximately 8 weeks after beginning treatment, subjects will return to the clinical research office for an in person visit. An interview and vital signs will be conducted. Height and weight and PVR will be measured. Pad weights will be measured, and the 3 day voiding diary will be collected and reviewed. Blood will also be drawn to measure serum AST, ALT, and total bilirubin. Questionnaires will also be completed and concomitant meds and adverse events including any vaginal bleeding, discharge, infections and/or spotting, will be assessed and recorded. Subjects will also be instructed to complete a 24 hour pad weight and 3 day voiding diary in the week preceding their next study visit. A 30 day supply of study drug will be dispensed with administration instructions.

Study Visit 5: Week 12, Clinic Visit

Approximately 12 weeks after beginning treatment, subjects will return to the clinical research office for an in person visit. An interview with vital signs will be conducted. A focused physical exam will be done. Gynecological pelvic exam will only be done at this visit if clinically indicated. Urine dipstick will be done and PVR will be measured. Height and weight will be measured. 24 hour pad weights and 3 day voiding diaries will be collected/reviewed. Blood will also be drawn to measure laboratory values as outlined in Table 1. UPP, Bladder Stress Test, and MRI will be performed at end of treatment, questionnaires will be administered, and concomitant medications/adverse events will be assessed and recorded. All study medication will be collected and accounted for.

Study Visit 6: Week 16, Telephone/mailed questionnaire visit

Approximately 4 weeks after study drug treatment has ended, subjects will be contacted by phone to assess for concomitant meds and adverse events. Subjects will also be instructed to complete and return mailed questionnaires.

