8. STUDY PROCEDURES/EVALUATIONS

Please see Table 1 Schedule of Measures for an outline of the timing of the study procedures. Please see Appendix A, B, C, D, E for outcomes measures.

Interview with Vital Signs

All potential subjects will be interviewed/assessed to confirm inclusion/absence of exclusion criteria. A review of systems will be completed, concomitant medications will be assessed, and vital signs (temperature, blood pressure, pulse and respirations) will be assessed. Laboratory results will also be reviewed at specified time points as outlined in Table 1.

History

A detailed history will include review of gravida, prior abortions, parity, deliveries, and history of gynecological conditions and/or cancer.

Focused Physical Exam

A standard brief physical exam will be done. This will include a gynecological pelvic exam and visual skin exam with specific attention to androgenic changes.

Urinalysis

A clean catch midstream voided urine specimen will be obtained, and evaluated by urine dipstick. If results or clinical symptoms indicate, the specimen will be sent for culture and the patient will receive appropriate treatment for UTI per standard of care.

24 Hour Pad Weight Test

The 24-hour pad test should be completed during 1 day of each scheduled 3-day diary. Subjects will be instructed to record pad weight on a day that is typical for them in terms of activity level and fluid intake. Subjects should be given one type of incontinence pad at the clinic. They may choose from a "light" pad or a "heavy" pad, but the pads dispensed **MUST** be used for the 24-hour test. Subjects should receive 8 incontinence pads for use during each 24-hour test period.

Urethral Pressure Profile (UPP) and Bladder Stress Test

To conduct the UPP and Bladder Stress Test, a urodynamic catheter will be placed and the bladder will be filled with 300 ml of fluid, such as saline. UPP will be performed. Subjects will be instructed to perform a provocative maneuver to increase abdominal pressure (cough, Valsalva, or similar event). Urine loss during this event indicates a positive stress test.

Ultrasound Bladder Scan

Subjects will be asked to void, and the volume of urine remaining in the bladder after voiding (post void residual) will be measured via bladder ultrasound scan.

Mammogram

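### Vaginal bleeding, discharge, infection and spotting are named in the adverse-event assessment at Weeks 4 and 8 but not at Baseline, Week 1, Week 12 or Week 16, so prompting is uneven in a single-arm study

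*Combined protocol and SAP*

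**What the plan says.** Section 7.1 describes the adverse-event assessment visit by visit.

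- Visit 1 (Baseline): "Concomitant medications and adverse events, will be assessed and recorded".
- Visit 2 (Week 1): "Approximately 1 week after beginning treatment, subjects will be contacted by phone to assess for concomitant meds and adverse events".
- Visit 3 (Week 4): "concomitant meds and adverse events, including any vaginal bleeding, discharge, infections and/or spotting, will be assessed and recorded". Visit 4 (Week 8) repeats the phrase, differing only by a comma.
- Visit 5 (Week 12): "concomitant medications/adverse events will be assessed and recorded".
- Visit 6 (Week 16): "Approximately 4 weeks after study drug treatment has ended, subjects will be contacted by phone to assess for concomitant meds and adverse events".

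Three other parts of the protocol bear on the point.

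- **Diary.** Section 8 asks women to note vaginal discharge or spotting on the 3-day voiding diary. The Appendix E form has a colour column (red and brown among the codes) and an amount column (spotting among the codes). Table 1 schedules the diary at Baseline and Weeks 4, 8 and 12, and not at Week 16.
- **Definition.** Section 9.1.1 gives one adverse-event definition and one collection period, from consent to 28 days after treatment. It treats conditions present at screening as baseline unless they deteriorate.
- **Pelvic examination.** Of the focused physical exam, Section 8 says "This will include a gynecological pelvic exam and visual skin exam", and Table 1 schedules that exam at Baseline and Week 12. For Week 12, Section 7.1 says "Gynecological pelvic exam will only be done at this visit if clinically indicated".

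**The concern.** A direct question about a named symptom generally elicits more reports than a general question about adverse events. If the named question is put at two contacts and not at the others, the number of events found depends partly on when a woman was asked.

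Two consequences are possible. A symptom that predates treatment but is first asked about by name at Week 4 may be entered as new. An event after Week 8 may be missed if neither the general question nor the diary picks it up.

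In a randomised trial both arms would share this pattern. Here there is one arm, and no comparator is exposed to the same change in prompting.

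The protocol itself treats this as a safety area: it sets an endometrial thickness limit at entry, uses MRI endometrial thickness as a safety measure, and adds discharge columns to the diary.

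**Working it through.** The plan states no figure on this point, so there is nothing to reproduce. The check is a comparison of the visit texts, followed by a day count.

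**Step 1. Sources of information at each contact** (Section 7.1, Table 1, Section 8, Appendices A to E)

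| Contact | Named in adverse-event assessment | Diary reviewed | Other relevant sources |
|---|---|---|---|
| Baseline | No | Yes, 3 days | Interview with review of systems, gynecological history, pelvic exam |
| Week 1, phone | No | No | None specific |
| Week 4 | Yes | Yes, 3 days | Interview with review of systems |
| Week 8 | Yes | Yes, 3 days | Interview with review of systems |
| Week 12 | No | Yes, 3 days | Interview with review of systems, focused exam, MRI |
| Week 16, phone and mail | No | No | None specific |

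The mailed questionnaires do not fill the Week 16 gap: the forms in Appendices A to D have no item on vaginal bleeding, discharge, infection or spotting.

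**Step 2. Days without the named prompt.** Convention: a prompt at a clinic visit covers the time since the previous clinic visit, so the Week 4 and Week 8 prompts together reach back to the first dose.

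- Days from first dose to Week 16: 16 × 7 = 112. Days covered: 8 × 7 = 56.
- Treatment period: 12 × 7 = 84 days. Not covered: 84 − 56 = 28, and 28/84 = 33%.
- After crediting the 3 Week 12 diary days: 28 − 3 = 25, and 25/84 = 30%.
- With follow-up: 112 − 56 = 56, and 56/112 = 50%. After the same credit: 53/112 = 47%.
- With up to 21 screening days added, since collection starts at consent: (133 − 56)/133 = 77/133 = 58%. After crediting the Baseline and Week 12 diaries (6 days): 71/133 = 53%.

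**Step 3. What the diary can and cannot do.** Before Week 12 it samples 3 of about 28 days (3/28 = 11%). It captures bleeding only through the colour and amount of discharge and has no infection item. The documents do not say whether a diary entry is to be recorded as an adverse event. Section 10 reports safety by adverse events, and Section 10.1 plans no analysis of the discharge columns.

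**The case against.** The strongest reply is that the named phrase only illustrates what to ask, and that the protocol has other safeguards.

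- **The diary runs in the same form from before dosing to end of treatment.** This stands. A reader of Section 7.1 alone might infer that these symptoms are sought at Weeks 4 and 8 and nowhere else. Section 8 and Appendix E show otherwise for Baseline and Week 12. A like-for-like comparison of discharge and spotting from Baseline to Week 12 exists, on 3 days per visit.
- **Baseline has more than the diary.** This also stands. A gynecological history, a pelvic exam and a review of systems make it less likely that a long-standing symptom is first discovered at Week 4, though none of these texts names current discharge or spotting.
- **Staff ask about adverse events at every contact.** This stands too. A reader might infer that events after Week 8 depend on women volunteering them. Section 7.1 instead has staff assess adverse events in person at Week 12 and by phone at Week 16. What is missing is the named prompt.
- **One definition applies throughout.** Section 9.1.1 settles this. The wording difference affects how thoroughly events are sought, and does not alter what qualifies.
- **The half-of-the-study figure includes post-treatment weeks.** This is fair, because Section 10 reports adverse events during treatment. The 33% figure is the more relevant one for that report. The follow-up weeks still matter because Section 9.1.1 collects events there.
- **Endometrial effects have an objective check.** MRI thickness at Baseline and Week 12 is a safeguard, but it does not record bleeding, discharge or infection.

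These replies narrow the point. They leave the interval between Weeks 8 and 12 outside the diary days, and all of Weeks 12 to 16, without a named prompt.

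**Conclusion.** The point holds as one of uneven prompting. The named question is given at two of six contacts. Under the stated convention, 28 of 84 treatment days (33%, or 30% after the Week 12 diary) and 56 of 112 days with follow-up (50%, or 47%) lack it. These shares rest on the visit schedule and on the assumption that each prompt covers the interval since the previous clinic visit.

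Three stronger conclusions should not be drawn. First, a reader might convert the day shares into a percentage of missed events. That needs a capture rate for general versus named questions, and the documents give none, so the size of any under-count is unknown. Second, a reader might expect a spurious decline in events with longer exposure. Uneven prompting could produce one, but the plan has no analysis of adverse events by visit, so it would arise only if the data were presented that way. Third, a reader might infer that the Week 12 wording would leave women unexamined. The diary review, interview and MRI still take place then, and the effect on examination is speculative.

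The pelvic examination is a separate inconsistency: Section 8 with Table 1 and the Visit 5 text in Section 7.1 describe the Week 12 exam differently and must be reconciled.

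The change is worth making because it is cheap and because, in one arm, no comparison can offset the unevenness.

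**What to change.** 1. Use the Visit 3 and Visit 4 wording at every contact: at Visit 1 before the first dose, and at Visits 2, 5 and 6. At Visit 1, record the onset date, so that a symptom already present at screening is held as a baseline condition under Section 9.1.1. Under the day count above, Visits 5 and 6 bring coverage to 56 + 28 + 28 = 112 of 112 days. Visit 2 adds no days but makes the wording uniform.
2. State in Section 8 or 9.1.1 that diary entries of discharge or spotting are reviewed at the visit and assessed for recording as adverse events.
3. In Section 10, report the number of women with onset or worsening of these events after the first dose.
4. Reconcile the Section 7.1 text on the Week 12 pelvic examination with Section 8 and Table 1.

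The cost is one existing phrase added to contacts that already take place, a matching line on the CRF, and a sentence or two in the safety text. The downside is a slightly higher count of minor events.

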7.2 EARLY TERMINATION

Subjects may withdraw from the study voluntarily. In addition, if the PI determines that continued participation might present a safety risk for the subject then the PI may withdraw the subject from the study. Those subjects who receive study drug will be followed for 28 days after stopping study participation. Every effort will be made to obtain all end of treatment measures as outlined in (Table 1.Visit 6) in the event that a subject withdraws, or is withdrawn, from the study before completing treatment.

8. STUDY PROCEDURES/EVALUATIONS

Please see Table 1 Schedule of Measures for an outline of the timing of the study procedures. Please see Appendix A, B, C, D, E for outcomes measures.

Interview with Vital Signs

All potential subjects will be interviewed/assessed to confirm inclusion/absence of exclusion criteria. A review of systems will be completed, concomitant medications will be assessed, and vital signs (temperature, blood pressure, pulse and respirations) will be assessed. Laboratory results will also be reviewed at specified time points as outlined in Table 1.

History

A detailed history will include review of gravida, prior abortions, parity, deliveries, and history of gynecological conditions and/or cancer.

Focused Physical Exam

A standard brief physical exam will be done. This will include a gynecological pelvic exam and visual skin exam with specific attention to androgenic changes.

Urinalysis

A clean catch midstream voided urine specimen will be obtained, and evaluated by urine dipstick. If results or clinical symptoms indicate, the specimen will be sent for culture and the patient will receive appropriate treatment for UTI per standard of care.

24 Hour Pad Weight Test

The 24-hour pad test should be completed during 1 day of each scheduled 3-day diary. Subjects will be instructed to record pad weight on a day that is typical for them in terms of activity level and fluid intake. Subjects should be given one type of incontinence pad at the clinic. They may choose from a "light" pad or a "heavy" pad, but the pads dispensed **MUST** be used for the 24-hour test. Subjects should receive 8 incontinence pads for use during each 24-hour test period.

Urethral Pressure Profile (UPP) and Bladder Stress Test

To conduct the UPP and Bladder Stress Test, a urodynamic catheter will be placed and the bladder will be filled with 300 ml of fluid, such as saline. UPP will be performed. Subjects will be instructed to perform a provocative maneuver to increase abdominal pressure (cough, Valsalva, or similar event). Urine loss during this event indicates a positive stress test.

Ultrasound Bladder Scan

Subjects will be asked to void, and the volume of urine remaining in the bladder after voiding (post void residual) will be measured via bladder ultrasound scan.

Mammogram

Mammography is the process of using low-energy X-rays to examine the human breast, which is used as a diagnostic and screening tool. The goal of mammography is the early detection of breast cancer, typically through detection of characteristic masses and/or microcalcifications.

Magnetic Resonance Imaging(MRI)

MRI will be done at baseline and end of treatment to observe changes in pelvic floor muscles along with the thickness of the endometrium (mm). Quantitative assessments may include the area of the levator, the anteroposterior and transverse diameters, and/or other relevant parameters. Endometrial thickness can accurately be assessed by MRI (Stanislavsky, Weerakkody, et al., 2015; Nakamura et al., 2014); therefore, it is being used as a safety assessment in this study.

Medical, Epidemiological and Social Aspects of Aging (MESA) Questionnaire

The MESA questionnaire measures severity of specific types (stress, urgency, mixed) of urinary incontinence (UI). Two subscales, the urgency UI (6 items) and the stress UI (9 items). Test-retest reliability on “any incontinence” is high (agreement coefficient = .89). Validity (agreement between self-report on the MESA and clinician’s assessment) = 87% in women. The MESA questionnaire has demonstrated agreement on incontinence = 79% and 69% and 72% accuracy in predicting urodynamic diagnosis of stress UI and uninhibited detrusor contraction (Herzog, 1990a; Herzog, 1990b).

3 Day Voiding Diary

Subjects will record each episode of urinary leakage and record its severity. Subjects will also be asked to record urinary frequency, and urgency. Urine volume will also be recorded. 3 day bladder diaries are reliable measures of mean number of UI episodes/day, UI type, mean voids/24 hours, and mean voids during sleeping hours. 2-week test-retest results correlate with diurnal micturition ($r=.89$, $p<0.001$) and UI episodes ($r=.91$, $p<0.001$). Compared to participant recall of the previous week, Spearman rank correlation = .57 for voiding frequency and .70 for UI episodes (Brown, 2003; Locher, 2001; Wyman, 1988). For this study, any episode of vaginal discharge or spotting will also be recorded on the diary.

Patient Global Impression of Improvement (PGI-I)

PGI-I is a global rating of improvement using 7-point scale. Construct validity was established in two randomized controlled studies ($n=1,133$ subjects) of drug treatment for predominant stress incontinence (Wagner, 1996; Yalcin, 2003).

Patient Global Impression of Severity (PGI-S)

PGI-S is a global rating of symptoms severity using a 7 point scale (Yalcin, 2003).

UDI-6 and IIQ-7

The Urogenital Distress Inventory (UDI-6) and Incontinence Impact Questionnaire (IIQ-7) assess symptom distress and the impact of urinary incontinence on daily life. The

urogenital distress inventory (UDI) and incontinence impact questionnaire (IIQ) were both developed to assess the impact of UI on HRQoL (Shumaker, 1994; Wyman, 1987). Short versions of the UDI and IIQ, UDI- 6, and IIQ-7, were developed to reduce the respondents' burden. The UDI-6 and IIQ-7 are both "A grade" recommended by the Fourth International Consultation on Incontinence (Shumaker, 1994; Wyman, 1987; Uebersax, 1995; Staskin, 2008).

Female Sexual Function Index (FSFI)

The FSFI is a 19-question validated tool evaluating sexual function in several domains: libido, arousal, lubrication, orgasm, satisfaction and pain (Rosen et al, 2000). Each subdomain is scored separately and the total score is calculated.

